### 6.1.1 Dosing regimen

All eligible patients will be randomized starting from Cycle 1 Day 1 to receive either:

- Fulvestrant + ribociclib
- Fulvestrant + placebo

Ribociclib or placebo will be given orally once daily on days 1-21 of each 28 day cycle. Days 22-28 will be a “rest” period from dosing with ribociclib or placebo.

Fulvestrant will be administered intramuscularly into the buttocks slowly (1-2 minutes per injection) as two 5 mL injections, one in each buttock, on Cycle 1 Day 1 (C1D1), Cycle 1 Day 15 (C1D15), Cycle 2 Day 1 (C2D1) and every 28 days thereafter (i.e., the first day of each 28 day cycle) as per the (FASLODEX® [prescribing information](#)). There will be no “rest” in the fulvestrant schedule.

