##### **Meal considerations for sparse PK collection**

- Only for the sparse PK group, the meal condition (fasting, low fat, high fat) must be recorded on the eCRF **within ± 30 minutes of the dose** on C1D15 and C2D15. The meal condition is an estimate; however guidance is provided below.
- On C1D15 and C2D15, when PK is paired with ECG assessments, patients may consume breakfast only after fasted pre-dose blood samples (fasting glucose, fasting lipid profile) have been collected.
- Pre-dose PK should be collected approximately 24 hrs after the last dose (± 2 hrs) and immediately before the next dose.
- A high-fat meal typically contains 800-1000 calories with approximately 50% of the calories coming from fat (500-600 calories) (FDA Guidance for Industry for Food-effect Bioavailability and Fed Bioequivalence Studies, December 2002). An example of a high-

fat meal could be two eggs, 2 slices of bread, 1 tablespoon butter, 1 tablespoon jelly, 3 strips of bacon, 4 ounces of hash brown potato, and 8 ounces of whole milk. A low-fat meal could be approximately 300-500 calories with approximately 25% of the calories coming from fat (75-125 calories) and could include 2 slices of bread, 1 tablespoon light fat margarine, 1 tablespoon jelly, and 8 ounces of skim milk ([USDA National Nutrient Database for Standard Reference, 2010](#)).

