## 7 Visit schedule and assessments

### 7.1 Study flow and visit schedule

[Table 7-1a](#) and [Table 7-1b](#) list all of the assessments and indicates with an “X” the visits when they are performed. All data obtained from these assessments must be supported in the patient’s source documentation. The table indicates which assessments produce data to be entered into the database (D) or remain in source documents only (S) (“Category” column).

The following CRF(s) will be used as source document(s): local lab results.

Allowed visit windows are specified as follows:

- Screening assessments, apart from those listed below, must occur within 28 days of the randomization as per [Table 7-1a](#).
- Vital signs, physical exam, ECOG performance status, required labs, physical exam should be performed within 7 days of randomization.  
Note: If the physical examination was performed  $\leq 7$  days prior to the first dose of ribociclib/placebo, then they do not need to be repeated on Cycle 1 Day 1.
- In order for an accurate evaluation of baseline QTc, a total of three 12-lead ECGs will be performed at screening between -7 and -1 day.
- Randomization and Cycle 1 Day 1 should preferably occur on the same day. A maximum of a 3 days window between randomization and Cycle 1 Day 1 visit is permitted.
- For all visits (including PK visits C1D15, C2D1 and C2D15), a general  $\pm 3$  days visit window is permitted on assessments to take into account scheduling over public holidays, if not explicitly specified otherwise.
- For PK sampling, the samples may be obtained within the time window specified in [Table 7-6](#) and [Table 7-7](#).

- Radiological and patient reported outcome assessments must be performed as outlined in [Table 7-1a](#). A visit window of  $\pm 7$  days is allowed. (The whole body bone scan should be performed within 42 days or 6 weeks prior to randomization).
- Any screening assessments required within -7 to -1 days must be repeated if Cycle 1 Day 1 visit is delayed more than 7 days after randomization visit. Every effort should be made to follow the schedule outlined in [Table 7-1a](#).

Patients on placebo+fulvestrant that elect to transition to LEE011+fulvestrant arm or patient who continue with their current treatment (i.e. fulvestrant alone), should have safety assessments as per [Table 7-1a](#) and [Table 7-1b](#). Tumor assessments will continue as clinically indicated as described in [Section 7](#) (see [Table 7-1b](#)).

[figure not shown]

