**Table 7-7 Trough pharmacokinetic blood collection log**

Note: Trough PK sampling will be performed in all remaining patients Pre-dose on C1D15, C2D1 and C2D15.					
Cycle	Day	Scheduled Time Point Relative to Dosing	DRID No. for ribociclib/placebo	PK Sample No. for ribociclib/placebo	Blood Volume (mL)
1	15	Pre-dose a	201/2001 d	201	3
2	1	Pre-dose a	202	202	3
	15	Pre-dose a	203/2003 d	203	3
Unscheduled		Anytime b	NA	2001+	3
		PK samples related to a QTcF ≥ 501ms c	NA	2051+	3

a. Collect Pre-dose PK sample immediately before drug administration (approximately 24-hrs after the last dose and immediately before the next dose)

b. Unscheduled PK blood samples may be collected at any time for measurement of plasma drug concentrations if clinically indicated or at the Investigator's discretion and will be uniquely, sequentially numbered 2001, 2002, etc., for ribociclib/placebo

c. Unscheduled PK samples related to a QTcF ≥ 501 ms will be uniquely, sequentially numbered 2051, 2052, etc., ribociclib/placebo

d. The first DRID No is for the current dose, while the second DRID No is for the last dose the subject received prior to the collection of the PK sample

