3.10 Pharmacokinetic (PK) analyses

3.10.1 General principle

All PK analyses will be based on PAS set, unless otherwise specified.

Evaluable pre-dose concentrations satisfy the below conditions:

- Sample was collected before the current dose
- In addition, for pre-dose concentrations collected on Day 15 of any cycle
 - Patient had at least 10 consecutive days of ribociclib dosing (either 10 doses at 600 mg or 10 doses at 400 mg or 10 doses at 200 mg) immediately prior to the pre-dose collection. Ten consecutive doses are expected to provide adequate time to reach steady state for ribociclib at 600 mg and after dose reduction.
 - The PK collection was done at 24 ± 2 hours after the previous dose on Day 14 of the corresponding cycle.
 - Patient did not vomit within the first 4 hours following the last dose (confirmed using the records of date/time of PK sample collection and dosing).
 - the concentration has not been flagged for exclusion by the pharmacokineticist

Evaluable post dose 2h, 4h, 6h concentrations on Day 15 of any cycle satisfy the below conditions:

- Patient had at least 10 consecutive days of ribociclib dosing (either 10 doses at 600 mg or 10 doses at 400 mg or 10 doses at 200 mg) immediately prior to the PK collection.
- The PK collection was done within ± 15 minutes window of 2 hours after the Day 15 dosing for the post 2h concentration
- The PK collection was done within ± 30 minutes window of 4, 6 hours after the Day 15 dosing
- Patient did not vomit within the first 4 hours following the current dose.
- the concentration has not been flagged for exclusion by the pharmacokineticist

Only evaluable PK concentrations which are not flagged for exclusion will be used for figures, summaries, and statistical analysis. Concentration listings will include all concentrations, with flags indicating those excluded from analyses.

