3.10.2 PK concentrations

PK concentrations of ribociclib and LEQ803 at C2D1 will be summarized for fulvestrant+ ribociclib arm.

In addition, ribociclib and LEQ803 steady state concentrations (i.e., Cycle 1 Day 15 and Cycle 2 Day 15 concentrations) will be also summarized by ribociclib dose level, visit, and timepoint. Patients will be classified into the following dose groups at each visit (C1D15 and C2D15) and timepoint:

- RIBO600: consists of all patients who provided evaluable concentrations after receiving at least 10 consecutive daily ribociclib doses of 600 mg immediately prior to the PK collection without a dose change or interruption.
- RIBO400: consists of all patients who provided evaluable concentrations after receiving at least 10 consecutive daily ribociclib doses of 400 mg immediately prior to the PK collection without a dose change or interruption.
- RIBO200: consists of all patients who provided evaluable concentrations after receiving at least 10 consecutive daily ribociclib doses of 200 mg immediately prior to the PK collection without a dose change or interruption.

Additional separate summaries of ribociclib and LEQ803 will be produced for Asian and non-Asian patients (based on race) at each visit (C1D15 and C2D15) by ribociclib dose level and timepoint.

Descriptive statistics of concentrations will include n, m (number of non-zero concentrations), mean, CV%, SD, median, geometric mean, geometric CV%, minimum and maximum). Coefficient of variation CV% is calculated as below:

$$100 \cdot (\text{SD} / \text{arithmetic mean})$$

Geometric CV% is calculated as follows from non-zero values:

$$CV(\%) = 100 \cdot \sqrt{\exp(\hat{\sigma}^2) - 1}$$

where $\hat{\sigma}^2$ denotes the variance of the log-transformed values.

All individual plasma ribociclib (and also LEQ803) concentration data will be listed for fulvestrant + ribociclib arm using the Full analysis set. The meal record will be listed using Full Analysis Set.

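### The Cycle 2 Day 1 PK sample is a post-rest concentration, not a 24-hour trough, and the SAP pools it across dose levels and times since last dose

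*Protocol*

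**What the plan says.** Protocol 6.1.1 fixes the schedule: "Ribociclib or placebo will be given orally once daily on days 1-21 of each 28 day cycle", followed by seven days off. The note to Table 7-7 places the samples: "Trough PK sampling will be performed in all remaining patients Pre-dose on C1D15, C2D1 and C2D15". Footnote a, attached to all three pre-dose samples there and to the pre-dose samples in Table 7-6, defines the timing: "Collect Pre-dose PK sample immediately before drug administration (approximately 24-hrs after the last dose and immediately before the next dose". Protocol 6.1.1.2 repeats it with a tolerance: "Pre-dose PK should be collected approximately 24 hrs after the last dose (± 2 hrs) and immediately before the next dose". Protocol 7.1 allows ±3 days for PK visits, and names C2D1 among them. The secondary objectives in the protocol summary also list C2D1 with the two Day 15 visits as days for characterising PK at steady state.

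In the primary-analysis SAP, Section 3.10.1 requires of every pre-dose sample that "Sample was collected before the current dose". The further conditions (10 consecutive daily doses at one level, 24 ± 2 h since the previous dose, no vomiting within 4 h) apply to Day 15 only. Samples flagged by the pharmacokineticist are also left out, but no criterion for flagging is given. Section 3.10.2 then states: "PK concentrations of ribociclib and LEQ803 at C2D1 will be summarized for fulvestrant+ ribociclib arm". Day 15 concentrations are instead split into 600, 400 and 200 mg groups.

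**The concern.** A collection rule that no patient on the planned schedule can satisfy leaves it unclear what the C2D1 value represents. Calling it a trough, or a steady-state value, invites a reader to set it beside the Day 15 troughs, which are a different quantity.

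The SAP then has no rule to keep the C2D1 summary homogeneous. A patient who took 600 mg through Day 21, one reduced to 400 mg, and one held from Day 15 who restarts at C2D1 would all enter the same mean and coefficient of variation. The last case is plausible on the protocol's own account: neutropenia typically appears by Day 15 (Section 1.2.1.2.1), haematology is tested that day (Table 7-1a), and Grade 3 neutropenia calls for interruption (Table 6-4). Concentration by time point is the stated secondary PK endpoint (Table 3-1), so the summary should have a definable meaning.

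**Working it through.** **Inputs.** Dosing days 1 to 21 of 28 (Protocol 6.1.1); ±3-day window (7.1); mean effective half-life 12.3 to 42.9 h and mean accumulation ratio 1.35 to 3.11 across 50 to 1200 mg, and geometric mean AUC0-24 of 23,600 ng·h/mL at 600 mg (1.2.1.2.3); LLOQ about 1 ng/mL (7.2.3.2). No half-life is given for 600 mg alone, so both ends of the range are used.

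**1. Interval since last dose.**
- Day 15: (15 − 14) × 24 = 24 h. The footnote's figure reproduces.
- C2D1 is day 29: (29 − 21) × 24 = 192 h. It does not reproduce; the difference is 168 h.
- With ±3 days: 5 × 24 = 120 h to 11 × 24 = 264 h. No allowed visit date gives 24 h.

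**2. Check of the half-life range.** Effective half-life = 24 × ln 2 / ln[R/(R − 1)]. R = 1.35 gives 12.3 h and R = 3.11 gives 42.9 h, so the protocol's range is internally consistent.

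**3. Ratio between pooled samples**, assuming mono-exponential decay: 2^(difference in gap / half-life).

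| Contrast at C2D1 | Difference | 42.9 h | 12.3 h |
|---|---|---|---|
| Last dose Day 21 vs Day 14 (8- vs 15-day gap), equal dose | 168 h | 15.1 | about 12,900 |
| Last dose Day 21 vs Day 18 (8- vs 11-day gap), equal dose | 72 h | 3.2 | about 58 |
| Extremes of the ±3-day window, equal dose | 144 h | 10.2 | about 3,340 |
| 600 vs 400 mg, equal gap, dose-proportional | none | 1.5 | 1.5 |

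**4. Approximate levels.** With k = ln 2 / half-life, the one-compartment steady-state trough is AUC × k × e^(−24k) / (1 − e^(−24k)).
- At 42.9 h: trough 805, 8-day value 805 / 15.1 = 53.3, 15-day value 53.3 / 15.1 = 3.5 ng/mL.
- At 12.3 h: trough 464, 8-day value 0.036, 15-day value below 0.001 ng/mL.

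At the short end both gaps lie below the LLOQ and would be recorded as zero, so the very large ratio there would not be visible in the table.

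**The case against.** **The SAP does not treat C2D1 as a trough.** It keeps C2D1 out of the steady-state summaries (3.10.2), out of the average steady-state trough (3.10.3.1) and out of the QTcF dose groups (3.10.3.2). This stands, and it limits the consequence to one descriptive table. A reader might infer that the exposure-response work is contaminated; the documents show that it is not.

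**Interrupted patients are already removed.** The additional sampling guidelines in Protocol 7.2.3.1 say that no PK sample is taken for a visit at which ribociclib is interrupted. That covers a patient still off drug at C2D1. It does not clearly cover one who resumes that day.

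**The pooled summary follows the protocol.** Section 10.5.4 asks only for concentrations by time point in the ribociclib arm, and no PK hypothesis is tested. This is correct, but the SAP saw a need for dosing conditions and dose groups at Day 15 and gives no reason to drop them at C2D1.

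**Little remains to change in conduct.** Amendment 4 ended PK collection, and the final-CSR SAP contains no PK analysis. This also stands, so new footnotes would govern no further scheduled sample.

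**Below-LLOQ handling is pre-specified.** Such values count as zero in the arithmetic mean and as missing in the geometric mean, and the number of non-zero values is reported. A reader might infer a strong upward bias in the geometric mean from long gaps. That depends on an intermediate half-life which the documents do not give. At 42.9 h only about 2% of 15-day samples would fall below the LLOQ (lognormal, 66% CV, median 3.5 ng/mL). At 12.3 h essentially all 8-day samples would as well.

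**Conclusion.** Two points are certain from the text. The 24-hour instruction and the steady-state label conflict with the 21/7 schedule at C2D1, where the interval is about 192 h. The SAP also leaves C2D1 without any condition on prior dosing or time since last dose, and pools all doses.

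The size of the mixing is uncertain. It rests on mono-exponential decay and on half-lives that are dose-level means, not limits for individuals. The 15-fold figure belongs to one contrast, 8 versus 15 days at equal dose and 42.9 h. A reader might take it as a minimum for the pool, but three extra days off drug give about 3-fold at that half-life, and a 600 versus 400 mg difference about 1.5-fold. Nor can it be said that the C2D1 mean would mainly reflect holds and reductions, because the documents give no frequency of either in Cycle 1.

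This is a minor point confined to one descriptive summary of a secondary PK endpoint, but it is worth correcting because the remedy is cheap.

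**What to change.** **Protocol.** Reconcile footnote a of Tables 7-6 and 7-7, the matching sentence in 6.1.1.2 and the steady-state wording in the protocol summary with the schedule in 6.1.1. Label C2D1 a post-rest concentration.

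**SAP 3.10.1 and 3.10.2.** This is where the working change lies, since collection has ended.
- Define an evaluable C2D1 sample from recorded dosing: at least 10 consecutive doses at one level up to the planned last dose of Cycle 1, with the actual time since last dose inside a stated window. Accepting the whole ±3-day range would by itself leave about a 10-fold spread at 42.9 h, so the window should be chosen deliberately.
- Summarise C2D1 by dose level, as for Day 15, with the distribution of time since last dose and the number below the LLOQ.
- Keep excluded values, flagged, in the listings.

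**Cost.** Wording changes and one re-run table. Somewhat fewer C2D1 samples would enter the summary, and the 400 and 200 mg groups may be small.

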### **Additional guidelines for pharmacokinetic sampling/ECG**

[figure not shown]
[figure not shown]
On days with PK sampling and/or ECG testing (collection days are outlined in [Table 7-1a](#)), the following additional guidelines must be followed:

[figure not shown]
[figure not shown]
- Pre-dose ECGs must be done **first, prior to pre-dose PK sampling and prior to dosing**.
- The time of PK collection and the time the study medication was taken must be precisely recorded in the eCRF.
- Furthermore, the date and time the study medication was taken on the **day before** the PK collection must be precisely recorded in the eCRF.
- Post-dose ECGs and/or PK samples should be collected after dosing of the study treatment. ECGs must be done prior to PK sampling.
- ECG and PK sample collection will be performed according to [Section 7.2.3](#) and [Table 7-5a](#) and [Table 7-5b](#), [Table 7-6](#) and [Table 7-7](#).
- In the case where ribociclib/placebo is being temporarily interrupted or has been permanently interrupted, no PK samples will be collected for the corresponding visit.

[figure not shown]
[figure not shown]
#### **7.2.3.2 Analytical method**

[figure not shown]
[figure not shown]
Plasma concentrations of ribociclib (and any relevant metabolite such as LEQ803) will be measured using validated liquid chromatography-tandem mass spectrometry (LC-MS/MS) methods with a lower limit of quantification (LLOQ) of approximately 1.0 ng/ml for ribociclib. Sample analysis will be performed by Novartis or a Novartis designated laboratory using validated methods. Any results below the LLOQ and any missing samples will be recorded accordingly.

Leftover plasma from analysis may be used for [REDACTED] other bioanalytical purposes (e.g., cross check between different sites, stability assessment).

### 7.2.6 Patient reported outcomes

The European Organization for Research and Treatment of Cancer's core quality of life questionnaire (EORTC-QLQ-C30, version 3.0), the EuroQoL 5-level instrument (EQ-5D-5L, tablet version), and the Brief Pain Inventory-Short form questionnaire (BPI-SF, copyright 1991) will be used to evaluate patient-reported outcome measures of health-related quality-of-life, functioning, disease symptoms, treatment-related side effects, global health status, and cancer-related pain. The EORTC QLQ-C30, EQ-5D-5L, and BPI-SF are recognized reliable and valid measures (Aronson 1993, Rabin 2001, Cleeland 1994) frequently used in clinical trials of patients with advanced or metastatic breast cancer.

All patient-reported outcome (PRO) measures (eg, EORTC QLQ-C30, EQ-5D-5L, and BPI-SF) will be administered before any study drug administrations at the visits indicated in Table 7-1a and Table 7-9. Collection of PRO measures have a  $\pm 7$  day window unless otherwise indicated.

All PRO data will be collected using an electronic tablet device and should be administered in the patient's local language at the beginning of the study visit prior to any interaction with the study investigator including any tests, treatments or receipt of results from any tests to avoid biasing the patient's perspective. Patients should be given sufficient space and time to complete all study questionnaires and all administered questionnaires should be reviewed for completeness. If missing responses are noted, patients should be encouraged to complete any missing responses. Attempts should be made to collect responses to all questionnaires for all patients, including from those who discontinue prior to the study evaluation completion visit, however, if patients refuse to complete questionnaires, this should be documented in study source records. Patient's refusal to complete study questionnaires are not protocol deviations.

The use of electronic data collection of clinical outcome assessments (eCOA), including PROs, has been endorsed as standard. The use of both eCOA and paper PRO collection of the same

COA measure in a single study is not endorsed. However, paper PRO may be utilized as a backup should there be a failure with the electronic version/system.

Paper should be used as a last resort option. In case of any issues with the device use, which cannot be resolved within the visit time window, PRO questionnaires could be completed on paper form and transcribed into the tablet at the next possible opportunity.

All questionnaires should be administered in the patient’s local language prior to any interaction with the study investigator. This is to avoid potentially biasing patients or their responses to study questionnaires.

Completed questionnaires, including both responses to the questions and any unsolicited comments written by the patient, must be reviewed and assessed by the investigator before the clinical examination for responses which may indicate potential AEs or SAEs. This review should be documented in study source records.

If an AE or SAE is confirmed then the physician should record the event as instructed in [Section 8](#) of this protocol. Investigators should not encourage the patients to change responses reported in questionnaires.

**Following protocol amendment 4, no additional PRO measures should be collected from any patients.**

[figure not shown]
**Table 7-9 Patient reported outcomes collection plan**

Patient Questionnaire	Cycle	Visit	Time
EORTC QLQ-C30 EQ-5D-5L BPI-SF	Screening	-28 to Day -1	Prior to any clinical assessments, drug dosing or diagnostic testing
	Subsequent cycles	Every 8 weeks after randomization during the first 18 months, then every 12 weeks until 36 months. Thereafter, PRO collection should align with periodic efficacy assessments until disease progression, death, withdrawal of consent, loss to follow-up, or subject/guardian decision	
	End of treatment	Day of EOT visit	
	Efficacy follow-up	Continue collection every 8 weeks after randomization during the first 18 months and every 12 weeks thereafter until 36 months, then align with the efficacy assessments only in case end of treatment occurs for reasons other than death, lost to follow-up, withdrawal of consent, or disease progression	

**7.2.6.1 EORTC QLQ-C30**

The EORTC QLQ-C30 contains 30 items and is composed of both multi-item scales and single-item measures. These include five functional scales (physical, role, emotional, cognitive and social functioning), three symptom scales (fatigue, nausea/vomiting, and pain), six single items (dyspnea, insomnia, appetite loss, constipation, diarrhea and financial impact) and a global health status/QoL scale ([Aaronson et al 1993](#)).

All of the scales and single-item measures range in score from 0 to 100. A high scale score represents a higher response level. Thus a high score for a functional scale represents a high /

healthy level of functioning; a high score for the global health status / QoL represents a high QoL, but a high score for a symptom scale / item represents a high level of symptomatology / problems. All scoring will follow the scoring procedures defined by the EORTC Scoring Manual (Fayers et al 2001).

